1. SUMMARY

Sponsor Investigator: [name]
Sponsor: Baylor College of Medicine
Funding: Allergan
Product Name: Ceftaroline
Protocol Title: Phase 1/2 Trial of Ceftaroline for the Treatment of Hematogenously Acquired Staphylococcus aureus Osteomyelitis in Children
Clinical Phase: 1/2
Objectives:
Primary:

Evaluate the safety of ceftaroline in pediatric subjects 1 to 17 years of age (inclusive) with acute hematogenous osteomyelitis at the end of intravenous therapy.
Secondary:

Evaluate efficacy of ceftaroline in pediatric subjects with acute hematogenous osteomyelitis at the end of IV therapy, at the end of total therapy (anticipated to be at 4 to 6 weeks after enrollment), and at one year after enrollment.Evaluate clearance of S. aureus bacteremia if blood cultures initially positive.Assess proportion of patients with plasma levels of ceftaroline that exceed 1 µg/mL for over 60% of a dosing interval.
Study Design: This is a Phase 1/2, open-label, single-center study to determine safety and tolerability of ceftaroline in pediatric subjects 1 to 17 years of age (inclusive) with signs and symptoms of acute hematogenous osteomyelitis at the end of intravenous therapy. After informed consent/assent is obtained, ceftaroline will be administered intravenously. After the subject has been afebrile for at least 48 hours, has negative blood cultures, is clearly improving in general, is able to eat and drink, and is able to use or move the involved extremity, the subject may be switched to oral antibiotic administration.
Number of Subjects: 18 Children 1 to 17 years of age, inclusive. Each subject will receive ceftaroline. 2 subjects above 5 years old will be enrolled before the younger subjects are enrolled.
Planned Study Period: Approximately 60 months (funding approval to last subject last visit). 6 subjects/year enrollment is anticipated.
Treatment Duration with ceftaroline: Approximately 5 to 14 days.
Subject Participation: The duration of subject participation from signing the informed consent form will be up to 14 months (includes screening period, study drug administration, oral drug administration and a follow-up visit 12 months after the last dose of study drug). Baseline assessments for study eligibility will occur within 24 hours before the first dose of study drug except for Alkaline Phosphatase, Bilirubin, AST/ALT which will be obtained prior to administration of ceftaroline but the results may not be available. A minimum of 2 days (48 hours) of study drug administration is required to assess safety.

Test Product, Dosage, and Mode of Administration: IV ceftaroline fosamil **15 mg/kg** (or 600 mg if > 40 kg) infused over 120 (\pm 10) minutes q8h (\pm 1 hour) for children **2 years** of age – **17 years** of age (inclusive). IV ceftaroline fosamil **10 mg/kg** infused over 120 (\pm 10) minutes q8h (\pm 1 hour) for children from **1 year of age to < 2 years** (inclusive).

Isolate susceptibilities: The ceftaroline MIC of *S. aureus* isolates or other isolates such as Group A streptococcus, *Streptococcus pneumoniae* or *Kingella kingae* that are obtained from the patients with acute hematogenous osteomyelitis will be determined using Clinical and Laboratory Standards Institute (CLSI) methods. These will be performed in the CAP certified Infectious Disease Research Laboratory. CLSI interpretive breakpoints will be used to determine if the isolate is susceptible, intermediate or resistant to ceftaroline.

Oral Switch: A switch to one of the following open-label PO drugs is expected/allowed on or after EOIV assessments are completed and if criteria in Section 9.2 are met:

- PO clindamycin 13 mg/kg/dose q8h in subjects with proven MRSA infection due to clindamycin susceptible MRSA or if no pathogen is isolated.

OR

- PO cephalexin 25 to 33 mg/kg/dose q 8 hours in subjects with proven MSSA infection.

OR

- PO linezolid 600 mg q12h (Children > 12 years old) or 10 mg/kg q8h (children < 12 years old) in subjects with clindamycin-resistant MRSA pathogens or for patients with MRSA isolates who are unable to tolerate clindamycin.

Inclusion Criteria: Subjects are required to meet the following inclusion criteria:

1. Informed consent in writing from parent(s) or other legally acceptable representative(s) and assent from subject (if appropriate according to local requirements).
2. Male or female 1 to 17 years of age.
3. Suspected hematogenous SA osteomyelitis in a large bone (upper or lower extremities, pelvis) based on clinical findings and radiology results.
4. One to three sites of osteomyelitis with expectation that transition to oral antibiotics will be likely prior to discharge to complete IV therapy (The second or third site might be contiguous like a proximal tibia and distal femur but could also be at sites unrelated such as a distal femur and pelvic bone).
5. Female subjects who have reached menarche must have a negative urine pregnancy test.
6. Female subjects who have reached menarche and are sexually active must be willing to practice sexual abstinence or dual methods of birth control (eg, condom or diaphragm with spermicidal foam or gel) during treatment and for at least 28 days after the last dose of any study drug.
7. Sufficient IV access to receive medication.

Exclusion Criteria: Subjects must **NOT** meet any of the following exclusion criteria. Septic arthritis contiguous to the site of osteomyelitis is not an exclusion criterion.

1. Received more than 24 hours of IV antibiotics prior to enrollment.
2. More than three bones infected.
3. Disseminated infection or is admitted to the pediatric intensive care unit.
4. Underlying condition (excludes mild eczema or reactive airways disease).
5. Suspected or proven venous thrombosis or concern for endocarditis.
6. Requirement for other reasons for another antibiotic potentially active against organisms commonly causing osteomyelitis in children.
7. Creatinine clearance < 50 mL/min/1.73m² (calculated by the Schwartz formula).
8. AST or ALT > 3 times the upper limit of normal.
9. Neutropenia (<500 neutrophils/mm³).
10. Thrombocytopenia (<50,000 platelets/mm³).
11. Females who are currently pregnant or breast feeding.
12. Hypersensitivity reaction to any Beta-lactam antibiotic.
13. Has had an allergic reaction to ceftaroline in the past.

Safety: Adverse event and serious adverse event monitoring, vital signs and laboratory tests (CBC, BUN, Creatinine, Alkaline Phosphatase, Bilirubin, AST and ALT will be obtained within 24 hours prior to enrollment and weekly during ceftaroline treatment and at the completion of ceftaroline treatment). The Alkaline Phosphatase, Bilirubin, AST/ALT results may not be available prior to enrollment of the patient. We do not anticipate that the AST/ALT concentrations will be > 3 UNL but if they were to be this elevated, the subject will be dropped from the study immediately.

Efficacy:

- Clinical response by subject and by baseline pathogen at the conclusion of IV ceftaroline.
- Clinical outcome at the completion of total therapy (IV plus oral)
- Clinical outcome at one year after enrollment into study-long-term follow-up.

Pharmacokinetics: The pharmacokinetic (PK) outcome measures will include concentrations of ceftaroline, ceftaroline fosamil (prodrug), and ceftaroline M-1 (inactive metabolite) in plasma in subjects on days 2 to 5 of treatment (only one PK sample collected on days 2-5) 4 hours (+/- 30 minutes) after the end of the infusion (before the start of the next infusion). Efforts will be made to obtain 1 PK blood sample (approximately 0.6 mL) at steady state from all subjects who receive ceftaroline fosamil. PK samples may be collected after any infusion of ceftaroline fosamil on those days and before oral switch.

If purulent material is being obtained from bone or subperiosteal abscesses at surgery or via drainage by interventional radiology, we will attempt to obtain specimens for measurement of ceftaroline concentrations.

Statistics:

- Descriptive statistical methods will be used to summarize the demographic characteristics of the subjects as well as selected clinical features such as duration of fever or positive blood cultures, time until normalization of ESR and CRP.
- The proportion of children with plasma concentrations of ceftaroline that exceed 1 μ g/mL at 4 hours following a 2 hour infusion of ceftaroline dose will be determined.
- Safety analyses will be conducted on all subjects who received at least one dose of ceftaroline. The occurrence of adverse events especially diarrhea, rash and evidence of bone marrow suppression which are the most common adverse effects associated with cephalosporin antibiotics will be evaluated.

Table 1.1 - Schedule of Assessments and Procedures

Assessment or Procedure	Baseline ¹	Treatment					Follow-up
		Day 1	Days 2-14	End of IV Treatment (EOIV)	Week 2, Week 4, and Week 6 After Discharge ¹⁴	End of Antibiotic Treatment (EOT)	
Obtain Informed Consent/Assent	X						
Verify Inclusion/Exclusion Criteria	X						
Demographic Data	X						
Medical and Surgical History	X				X	X	X
Complete Physical Examination ³	X						
Brief Physical Exam ⁴	X	X	X	X	X	X	X
Ambulatory/Movement Status ⁵	X	X	X	X			
Height and Weight	X					X	X
Peak Temperature	X	X	X	X			
Prior and concomitant medications	X	X	X	X	X	X	X
Vital signs	X	X	X	X	X	X	X
Record adjunctive therapeutic procedures (if performed i.e. Surgery) ⁶					X		
Standard of Care Radiology Results					X		
Clinical outcome				X		X	X
AEs and SAEs	X	X	X	X	X	X	
CBC with differential ⁷	X		X	X			
Chemistries (BUN, Creatinine, Alkaline Phosphatase, Bilirubin, AST, ALT) ⁷	X		X	X			
CRP and ESR ⁸	X	X	X	X	X	X	
Direct Coombs test	X			X			
Urine pregnancy test ⁹	X					X	
CrCl calculation	X				If Clinically Indicated		
Standard of Care Blood Culture ¹⁰			X				
Blood for PK analyses ¹¹			X				
Standard of Care Purulent Material From Bone ¹²			X				
Drug administration ¹³		X	X	X	X		

Abbreviations: AE = adverse event; CBC = complete blood count; CrCl = creatinine clearance; CRP = C-reactive protein; ESR = erythrocyte sedimentation rate; SAE = serious adverse event.

- 1 Perform baseline assessments within 24 hours before first dose of IV study drug.
- 2 Interval history focusing on the use of the involved extremity. On Month 12 follow up interval problems such as pathologic fractures and growth disturbances will be evaluated only.
- 3 The presence of warmth, tenderness, swelling, erythema, and movement of the infected extremity will be recorded specifically. The circumference of the infected extremity taken at the location of point tenderness will be determined.
- 4 Involved extremity will be assessed as at enrollment, if possible. Most of the subjects are expected to have surgical incision and drainage procedures and thus assessing the extremity for swelling, erythema, warmth and tenderness may not be possible because of drains in place and large surgical dressings that cannot be removed.
- 5 The degree of the subject's ability to ambulate will be assessed if the osteomyelitis is in the lower extremity-i.e. walks unaided, able to bear weight, can walk aid using a walker, etc. The use of upper and lower extremities will be assessed in terms of movement and range of motion.
- 6 Any surgical procedures will be documented and the findings described.
- 7 CBC and chemistries . If not done for SOC, collect samples for research if clinically indicated.
- 8 CRP and ESR will be collected typically as part of standard of care. If not performed for SOC, collect samples for research if clinically indicated.
- 9 Perform test if subject is a female who has reached menarche. If a pregnancy test is positive post baseline, follow reporting requirements in Section 11.1.4.
- 10 Isolate susceptibilities will be performed on samples obtained from Pathology as per section 10.8.1.
- 11 Refer to section 10.9. PK samples may be collected 4 hours (+/- 30 minutes) after any infusion of ceftaroline fosamil (before the start of the next infusion) on days 2-5 and before oral switch.
- 12 If purulent material is being obtained from bone or subperiosteal abscesses at surgery or via drainage by interventional radiology, we will attempt to obtain specimens for measurement of ceftaroline concentrations.
- 13 Administer drug per Section 9.
- 14 Week 2 visit will occur only if the subject has been discharged prior to Week 2.

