6.1. Outcome Measures

Primary: Safety evaluations will be conducted in the children who have started treatment with ceftaroline. Assessments will include:

- AEs, SAEs, deaths, and discontinuations due to SAEs.
- Vital signs and laboratory parameters.

Secondary:

- Clinical response (the subject has been afebrile for at least 48 hours, has negative blood cultures, is clearly improving in general, is able to eat and drink, and is able to use or move the involved extremity) at the end of parenteral therapy (approximately days 5 to 14) by subject and by baseline pathogens although *S. aureus* is expected to be the predominant pathogen.
- Clinical outcome (site of infection has complete resolution of pain, swelling and warmth and the patient is able to use the affected extremity normally and is back to normal activities) at the EOT and at the one year follow up visit.

- Clinical relapse within a year of enrollment in the study or the development of a pathologic fracture.

PK:

- Concentrations of ceftaroline fosamil, ceftaroline, and ceftaroline M-1 in plasma.
- If available, concentrations of ceftaroline fosamil, ceftaroline, and ceftaroline M-1 in purulent material such as bone or subperiosteal abscess or synovial fluid.

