7.8.2. Discontinuations Due to Insufficient Therapeutic Effect

Assessments and Procedures: A subject who is prematurely discontinued from study drug administration *due to insufficient therapeutic effect* should have EOIV (if on IV study drug) or EOT (if on PO drug) assessments conducted per Section 9, and undergo subsequent safety assessments at the 4 to 6 week follow up visit. If a subject is discontinued from IV study drug administration *due to insufficient therapeutic effect* and is switched to an alternative IV antibiotic, the alternative therapy should be recorded.

Clinical Outcome Assessment: A subject who is prematurely discontinued from study drug administration *due to insufficient therapeutic effect* should be assessed as a clinical failure on the day of discontinuation. Such a subject will be automatically assigned an outcome of clinical failure at all subsequent evaluation time points.

Reasons: Reason(s) for discontinuation from study drug administration *due to insufficient therapeutic effect* may include, but are not limited to, the following:

- Clinical Worsening: A subject who shows signs of clinical worsening may be prematurely discontinued from study drug administration at any time. If the Investigator deems the benefit-to-risk ratio of continuing study drug acceptable, study drug administration for at least 48 hours is encouraged before discontinuation. If the subject is improving clinically but the blood cultures are persistently positive for *S. aureus* for up to 5 days, ceftaroline can be continued at the discretion of the investigator.
- Lack of Clinical Progress: For a subject who is stable, yet does not show signs of improvement, the Investigator is encouraged to continue study drug administration at least 48 hours before such a subject is assessed as a clinical failure and the subject is prematurely discontinued from study drug.

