8.6. Adjunctive Surgical Procedures

Details of adjunctive surgical procedure(s) related to hematogenous SA osteomyelitis that are performed for any subject in this study will be collected and documented.

8.7.Treatment Compliance

Treatment compliance will be documented in the eCRF by recording the date, time, and whether or not each IV dose study drug was completely infused and, if applicable, whether or not each intended dose of PO drug was taken.

8.8.Accountability Procedures

It is the responsibility of the Pharmacist or designee to ensure that current records of study drug inventory and accountability are maintained. Records must be readily available for inspection.

Upon receipt of study therapy drugs, the Pharmacist or designee will acknowledge receipt, visually inspect the shipment, verify the number of vials shipped are received, and document the condition of the drugs received.

All study drugs provided by Allergan should be retained at the site until otherwise instructed in writing by Allegan. Upon completion of the study all used (vials), unused, and partially used IV study drugs will be shipped to a site designated by Allergan. Refer to the Pharmacy instructions or package insert for additional information.

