9.3. Study Days 2-14

The total duration of IV ceftaroline is dependent on the subject's response to therapy but 5-14 days is anticipated in most subjects. If the subject is able to switch to oral drug before Day 15, the procedures outlined for Day 15 (EOIV) should be performed. The rest of the visit schedule will be followed as described in Table 2.1.

- Study Drug Administration:

IV ceftaroline fosamil **15 mg/kg** (or 600 mg if > 40 kg) infused over 120 (\pm 10) minutes q8h (\pm 1 hour) for children **2 years of age – 17 years** of age (inclusive).

IV ceftaroline fosamil **10 mg/kg** infused over 120 (\pm 10) minutes q 8h (\pm 1 hour) for children from **1 year of age to < 2 years** (inclusive) until the subject transitions to oral therapy.

- Clinical Assessments – any time during study day (assessments will be performed for research unless they are already being performed per standard of care; exceptions are indicated):
 - Record concomitant medications (Section 8.3). For subjects who are being breast fed, record all medications taken by the lactating mother.
 - Record resting vital signs (pulse, blood pressure, and respiratory rate), and highest postdose temperature measured.
 - Record adjunctive therapeutic procedures (eg, surgeries).
 - Record standard of care radiology results.
 - Evaluate and record physical findings of hematogenous SA osteomyelitis (eg, warmth, tenderness, swelling, erythema, and movement of the infected extremity). Most of the subjects are expected to have surgical incision and drainage procedures and thus assessing the extremity for swelling, erythema, warmth and tenderness may not be possible because of drains in place and large surgical dressings that cannot be removed. The degree of the subject's ability to ambulate will be assessed if the osteomyelitis is in the lower extremity- ie. walks unaided, able to bear weight, can walk aid using a walker, etc. The use of upper and lower extremities will be assessed in terms of movement and range of motion.
 - Identify, assess, and record any new or ongoing AEs or SAEs
- Laboratory Assessments – any time during the study period if clinically indicated (assessments will be performed for research unless they are already being performed per standard of care; exceptions are indicated):
 - Collect CRP and ESR lab results, if clinically indicated.
 - Collect CBC with differential, BUN, and Creatinine, lab results, if clinically indicated.

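### Surgical drainage is expected in most children and recorded throughout, but no efficacy definition or analysis uses it, so a child needing repeat unplanned drainage on ceftaroline can still count as a responder

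*Combined protocol and SAP*

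**What the plan says.** **Surgery is expected and recorded.** Table 1.1 footnote 4 states: "Most of the subjects are expected to have surgical incision and drainage procedures". Footnote 6 adds: "Any surgical procedures will be documented and the findings described". Section 8.6 says: "Details of adjunctive surgical procedure(s) related to hematogenous SA osteomyelitis that are performed for any subject in this study will be collected and documented". Sections 9.1 to 9.7 each carry an instruction of the form "Record adjunctive therapeutic procedures (eg, surgeries", and 9.9 sends procedures to the eCRF.

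**The efficacy definitions contain no surgical condition.** Section 6.1 defines end-of-IV response by five clinical criteria, beginning "the subject has been afebrile for at least 48 hours, has negative blood cultures, is clearly improving in general"; the others are eating and drinking, and use or movement of the limb. Clinical outcome at EOT and one year is resolution of local signs with normal use and activity. Section 9.4 applies that outcome wording at EOIV as well, also without reference to surgery.

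**The analysis does not use surgery.** Section 12.5 and the Summary list "Clinical response by subject and by baseline pathogen at the conclusion of IV ceftaroline", then outcome at completion of therapy and at one year. Surgery is absent from the endpoints in 12.3 and from the features named in 12.1.

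**Failure is described in three places.** Under 7.8.2, a child taken off study drug for insufficient effect "should be assessed as a clinical failure on the day of discontinuation". Section 7.10 stops the study at two treatment failures without defining the term. Section 12.7 halts the study if two children do not improve as anticipated, and speaks of failures as children who have not responded as expected. None of the three mentions drainage.

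**The concern.** Persistent infection during ceftaroline can be met with another drainage procedure while the drug continues. If that works, the child may be afebrile for 48 hours with negative cultures by the end of IV therapy and so satisfy every criterion in 6.1. Nothing in the definition or the analysis would distinguish this child from one who recovered on ceftaroline after the initial drainage alone.

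With no control arm, nothing offsets the contribution of the later surgery, and readers will tend to attribute the response rate to the drug. The failure count is also affected, because two failures stop the study. In addition, 10.3 excludes worsening from lack of effect from SAE reporting, unless it is considered drug-related, on the ground that it is captured as an efficacy endpoint. No efficacy endpoint is written to capture repeat drainage during treatment. If classification is left until the 18 outcomes are known, it becomes a post hoc choice.

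**Working it through.** **1. The plan's own figure.** Section 6.2 gives A'Hern's single-stage design with null rate 0.50, alternative 0.80, type 1 error 0.05 and power 80%. I searched for the smallest n with P(X >= r | 0.50) <= 0.05 and P(X >= r | 0.80) >= 0.80, one-sided.

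- n = 16, r = 12: power 0.798.
- n = 17, r = 13: power 0.758.
- n = 18, r = 13: power 0.867. P(X >= 13 | 0.50) = (8568 + 3060 + 816 + 153 + 18 + 1)/2^18 = 12616/262144 = 0.048.

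The stated 18 reproduces and is not in dispute. The 13/18 cut-off is implied by 6.2 but not written there.

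**2. Effect of one child.** 1/18 = 5.6 percentage points. If 14/18 are counted as responders (77.8%, exact 95% CI 52.4 to 93.6) and two of them had repeat unplanned drainage, the rate without them is 12/18 (66.7%, CI 41.0 to 86.7). The first figure meets the cut-off and the second does not.

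**3. Effect on the chance of a positive result.** Assumptions: pi is end-of-IV response; the true rate without repeat drainage is 0.50; a share s of the remaining children is converted to responders by repeat drainage. The documents give no value for s, so a range is shown. Apparent rate = 0.50 + 0.50 × s.

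| s | Apparent rate | P(X >= 13 of 18) |
|---|---|---|
| 0 | 0.500 | 0.048 |
| 5% | 0.525 | 0.073 |
| 10% | 0.550 | 0.108 |
| 20% | 0.600 | 0.209 |
| 30% | 0.650 | 0.355 |
| 40% | 0.700 | 0.534 |
| 50% | 0.750 | 0.717 |

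**4. Effect of counting repeat drainage as non-response.** Take 0.80 as the rate under the present definition and let a share q of those responders have repeat unplanned drainage. The rate becomes 0.80 × (1 − q).

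| q | Rate | P(X >= 13 of 18) |
|---|---|---|
| 0 | 0.80 | 0.867 |
| 5% | 0.76 | 0.751 |
| 10% | 0.72 | 0.609 |
| 20% | 0.64 | 0.322 |

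The classification matters in both directions, which is a reason to show both figures rather than replace one with the other.

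**5. How the failure passages treat this child.** Under 7.8.2 failure follows discontinuation for insufficient effect; the listed reasons are open-ended and include clinical worsening, but stopping for worsening is optional. Section 7.10 does not refer to 7.8.2. Section 12.7 describes failure without requiring discontinuation. A re-drained child who stays on drug falls outside the wording of 7.8.2, may fall inside 12.7, and is undetermined under 7.10.

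**The case against.** **Surgery is part of treating this disease.** The protocol calls it adjunctive, and scoring outcome regardless of it is a legitimate treatment-policy choice. This stands for initial drainage. It does not settle how later, unplanned drainage for persistent infection should be read, and the plan does not state that choice.

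**A reader might infer that every re-drained child is automatically a responder and can never be a failure.** The documents do not support that. The investigator may judge worsening and stop the drug under 7.8.2, and 12.7 allows failure without stopping. What stands is that the classification is undefined.

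**A reader might also infer that persistent infection would appear nowhere in the results.** Section 12.1 plans summaries of fever duration, positive cultures and time to ESR and CRP normalization, and its list is not exhaustive; 6.1 includes relapse and pathologic fracture. These could show persistence, but they do not change who counts as a responder.

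**The probabilities are conditional.** Section 6.2 does not say what pi is, the primary endpoint is safety, 12.5 specifies no test, and s is assumed. If every non-responder were also a treatment failure under 7.10, the chance of completing 18 children with at most one failure would be only 0.001, 0.014 or 0.039 at rates of 0.60, 0.70 or 0.75, so the tabulated values would not be this trial's operating characteristics. The protocol does not equate the two terms, but the caution is fair.

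**Counting any drainage begun after 48 hours as non-success would be too broad.** It would catch first and staged procedures. The 48 hours in 7.8.2 only encourages continued drug before failure is called.

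**Operative blood loss could blur hemoglobin change from baseline in 12.4.** Direct Coombs at baseline and EOIV, the hemolysis evaluation in 10.9 and causality assessment already help, and few children are likely to be unoperated. Stratified tables would add little.

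**Conclusion.** The point holds as a gap in definition and analysis. A child with repeat, unplanned index-site drainage for persistent or worsening infection, who stays on ceftaroline and then meets the 6.1 criteria, can be counted as a responder, and that child's failure status is unresolved across 7.8.2, 7.10 and 12.7. The response rate can therefore be too high as a measure of ceftaroline.

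The certain part of the size is 5.6 points per child. The total is unknown. The range 0.07 to 0.72 against 0.048 holds only if pi is end-of-IV response, the true rate is 50%, and 5% to 50% of non-responders are converted. It should not be read as an estimate of the bias, nor as evidence that the bias will occur. The sample size is unaffected.

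**What to change.** **In 12.5:**

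- Tabulate index-site procedures by timing relative to the first ceftaroline dose, and as initial/planned or repeat/unplanned.
- Keep end-of-IV response and EOT outcome as defined. Add one pre-specified sensitivity analysis counting as non-successes the children who had repeat, unplanned index-site drainage for persistent or worsening infection after ceftaroline began. First and planned staged procedures are not reclassified.
- Report one-year outcome as defined, with such procedures listed alongside.

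**In 7.8.2, 7.10 and 12.7:** reconcile the passages so that it is clear whether such a child is a treatment failure. Which way this is settled is for the investigators.

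**Optional, in 12.4:** flag in the laboratory listing the children operated on between the baseline and EOIV samples.

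**Cost:** some plan wording and one extra table, largely from data already recorded. The eCRF should be checked for procedure date, site and reason, and planned versus unplanned needs a judgement recorded at the time. The sensitivity figure will be lower wherever such a child had counted as a success. This is an analysis classification, not a rule for care.
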